10.3 Severity of Adverse Events

All adverse events should be assessed for severity. The assignment of the severity/grading should be made by the investigator responsible for the care of the participant using the definitions in the table below:

Table 1: Severity Grading

Severity	Description
Mild	Does not interfere with routine activities.
Moderate	Interferes with routine activities.
Severe	Impossible to perform routine activities.
Life-Threatening	
Death	

N.B. A distinction is drawn between **serious** and **severe** AEs. Severity is a measure of intensity (see above) whereas seriousness is defined using the criteria in Section 10.2. Hence, a severe safety event need not necessarily be a “serious” safety event.

10.4 Assessment of “Causality” - Relationship to Study Treatment/Intervention

The assignment of the causality should be made by the investigator responsible for the care of the participant using the definitions in the table below:

Table 2: Definitions of Causality

Relationship	Description
Unrelated	There is no evidence of any causal relationship. N.B. An alternative cause for the AE should be given
Unlikely	There is little evidence to suggest there is a causal relationship (e.g. the event did not occur within a reasonable time after administration of the study medication). There is another reasonable explanation for the event (e.g. the participant's clinical condition, other concomitant treatment).
Possibly	There is some evidence to suggest a causal relationship (e.g. because the event occurs within a reasonable time after administration of the study medication). However, the influence of other factors may have contributed to the event (e.g. the participant's clinical condition, other concomitant treatments).
Probably	There is evidence to suggest a causal relationship and the influence of other factors is unlikely.
Almost certainly	There is clear evidence to suggest a causal relationship and other possible contributing factors can be ruled out.

Assessment of causality should be made based on known safety profile of IMOJEV®. In the case of discrepant views on causality between the treating investigator and others, the opinion of the treating investigator will never be downgraded and the REC will be informed of both points of view. Events that are assessed as being possibly, probably or almost certainly related will be reported as having a reasonable possibility of being

related, and events assessed as unrelated or unlikely will be reported as having no reasonable possibility of being related.

Assessment of causality should be made based on known safety profiles of IMP, or IB and known risk profiles of other drugs in the same class. If any doubt about the causality exists the local investigator should inform the LCTC who will notify the Chief Investigator. In the case of discrepant views on causality between the treating investigator and others, the opinion of the treating investigator will never be downgraded and the REC will be informed of both points of view.

10.5 Assessment of “Expectedness”

The Chief Investigator for the FlaviPrime study is responsible for determining whether a safety event is expected or unexpected, however a Chief Investigator will not assess their own participants, these participants will be assessed by the Medical Reviewer/Clinical Coordinator. There is no requirement for a reporting investigator to make an assessment of expectedness.

An event will be considered unexpected if it is not listed within the current and approved RSI for the study at the time of the event's onset. The nature, severity, or frequency of the event should be considered – if this is not consistent with that described for the type of event in the RSI the event should be assessed as unexpected.

Reference Safety Information / Information used to Assess Expectedness

Document name: Australian product information

IMOJEV® Japanese encephalitis vaccine (live, attenuated)

IMOJEV IB section “Adverse Effects” → “Data in adult populations”

The current version of the RSI documents applicable to this study will be made available to all clinicians involved in assessing the causality of adverse events, as well as the ethics committee and sponsor.

10.6 Time Period for Active Monitoring of Safety Events

IMPORTANT: Any safety events occurring after the end of the below described “active monitoring” period which meet the definition of serious and are recorded for this study must continue to be reported by sites to the LCTC in accordance with the timeframes and procedures described in section 11.3. The same processes established for SAEs within the active monitoring period should be followed for these events.

All new serious adverse events should be reported from the point of consent until 28 days after administration of the study vaccine. Depending on the nature of the event, the reporting procedures below should be followed. Any questions concerning adverse event reporting should be directed to LCTC in the first instance. Group 1 participants, who have their last study visit 9 days after vaccination, will be encouraged to report any adverse events that occur up to 28 days to the LUHFT CRU by phone.

AEs that occur during this timeframe should be reported to LCTC via the AE form. When reporting an increase in severity for an existing AE, the AE form should be changed to the new grade and the reason why (increase in severity) included. For a decrease in severity, no action is to be taken unless the symptoms have fully resolved (in which case the AE/SAE should be updated until resolved).

Although the period of adverse event monitoring in this study is 28 days, if the site team become aware of an adverse event that occurs outside this time and there are reasonable grounds to suspect the event is related to the vaccine or to participation in the study, it would be good practice to report this event to LCTC.

10.7 Notes on Safety Event Recording

The following events must be recorded for the purposes of the study:

- An exacerbation of a pre-existing illness
- An increase in frequency or intensity of a pre-existing episodic event/condition
- A condition (even though it may have been present prior to the start of the study) detected after study drug administration
- Continuous persistent disease or symptoms present at baseline that worsens following the administration of the study/study treatment
- Laboratory abnormalities that require clinical intervention or further investigation (unless they are associated with an already reported clinical event).
- Abnormalities in physiological testing or physical examination that require further investigation or clinical intervention
- Injury or accidents
- Pregnancy (See section 11 for more details)

Do not record:

- Medical or surgical procedures - the condition which leads to the procedure is the adverse event
- Pre-existing disease or conditions present before treatment that do not worsen
- Situations where an untoward medical occurrence has occurred e.g. cosmetic elective surgery
- Overdose of medication **without signs or symptoms***
- The disease being treated or associated symptoms/signs unless more severe than expected for the participant's condition

*N.B. If overdose occurred **with** resulting signs and symptoms that meet the protocol criteria for AE/SAE/SAR/RUSAЕ then they should be reported accordingly and the overdose highlighted to the LCTC team.

The events above do not need recording as the study population is healthy, and no disease is being treated by administration of this vaccine. The study is considered low risk. Any health event not related to the vaccine and not occurring during the study period (i.e. not an AE) is definitely unrelated to use of the vaccine, which is already in routine clinical use with a well understood safety profile.

11 Reporting of Pregnancy

If a participant or their partner becomes pregnant during study treatment or within 28 days following treatment, a Pregnancy Report Form must be completed and forwarded to the LCTC within 24 hours of learning of its occurrence and the investigational product will be permanently discontinued in an appropriate manner. (Should you need a paper copy of the Pregnancy Report Form please contact the Study Coordinator). Protocol-required procedures for study discontinuation and follow-up must be performed on the subject unless contraindicated by pregnancy.

IMOJEV® has not been studied in pregnancy, so if a participant were to fall pregnant, there are no data upon which to base an opinion as to the likely effects. However, in order to have an effect, the participant would have to actually be pregnant at the time of vaccine administration, or when vaccine related viraemia is present. This lasts up to 6 days after vaccination^[30], so a participant would have to fall pregnant very quickly after study enrolment for there to be any possibility of an effect on the pregnancy. The immune effects of the pregnancy could have an effect on the study data, but the risk of harm to the participant and the pregnancy would be extremely small. It should be noted that yellow fever vaccine (which is more toxic than IMOJEV) has been used in pregnancy during vaccination campaigns to contain outbreaks and there have not been reports of adverse effects on the fetus^[31].

On pregnancy outcome, the final Pregnancy Report Form should be completed and forwarded to LCTC 28 days after the outcome. The final Pregnancy Report Form is used to determine outcome, including spontaneous or voluntary termination, details of the birth, and the presence or absence of any birth defects, congenital abnormalities, or maternal and/or new-born complications. Pregnancy follow-up information on this form also includes an assessment of the possible relationship to the study intervention of any pregnancy outcome. Pregnancy outcomes should also be collected for the female partners of male participants participating in the study. Infants should be followed for a minimum of 8 weeks. Consent to report information regarding these pregnancy outcomes should be obtained from the mother prior to completion and faxing of the final Pregnancy Report Form. Any SAE experienced during pregnancy must be reported on the SAE form.

The LCTC will report all pregnancies to the study Sponsor and National Research Ethics Service.

Please Report

All pregnancies using the Pregnancy Report Form.

This should be reported within 24 hours of becoming aware.

ALSO

Pregnancy Outcomes must also be reported by completing the Final Pregnancy Report Form.

This should be completed 28 days following the outcome.

**Completed forms should be sent via SECURE email to
[contact]**

Sexually active women of child bearing potential (WOCBP) must use an effective method of birth control during the course of the study, in a manner such that risk of failure is minimised.

Before study enrolment, WOCBP must be advised of the importance of avoiding pregnancy during study participation and the potential risk factors for an unintentional pregnancy in accordance with the information contained in the Participant Information Sheet.

All WOCBP MUST have a negative pregnancy test within 72 hours before receiving treatment. The minimum sensitivity of the pregnancy test must be 25 IU/L or equivalent units of HCG. If the pregnancy test is positive, the subject must not be enrolled in the study. In addition, all WOCBP should be instructed to contact the investigator immediately if they suspect they might be pregnant (e.g. missed or late menstrual period) at any time during study participation.

Female participants who are of non-child bearing potential (i.e. due to being post-menopausal for at least 1 year (confirmed by FSH assessment) or permanently sterile following hysterectomy, bilateral salpingectomy, bilateral oophorectomy) will not be required to use contraception.

Female participants must be willing to use a highly effective method of birth control (i.e. contraceptive measure with a failure rate of <1% per year), from the time of Screening until 28 days after vaccination. Highly effective methods of contraception include:

- Placement of intrauterine device or intrauterine system
- Established use of oral, injected or implanted hormonal methods of contraception associated with inhibition of ovulation
- Additional barrier method (i.e. diaphragm or cervical vault cap used in conjunction with spermicide gel, foam, cream, film or suppository).
- Male sterilisation (with the appropriate post-vasectomy confirmation of surgical success). For female participants on the study, the vasectomised male partner should be the sole partner for that participant.
- Bilateral tubal ligation

Female partners of childbearing potential of male participants in the study must use an acceptable method of contraception from the time of screening until 28 days after vaccination. Other acceptable methods of contraception include:

- Any highly effective method of contraception listed above for female participants
- Progesterone-only oral contraception, where inhibition of ovulation is not the primary mode of action
- Cap, diaphragm, or sponge with spermicide

For participants who practice true abstinence, when this is in line with the preferred and usual lifestyle of the participant, contraceptive requirements do not apply. For participants who are exclusively in same-sex relationships, contraceptive requirements do not apply. Male participants with pregnant partners should use condoms from the time of vaccination and for two weeks afterwards.

[figure not shown]
Notification of Deaths

If the research team become aware of the death of a participant (whether related to the study or not) this should be notified to the LCTC using the appropriate CRF within 24 hours of becoming aware.

11.1 Reporting Procedures

All safety events which are recorded for the study should be reported following the procedures detailed below. The occurrence of a safety event may come to the attention of research staff during routine study visits, from the participant's notes, directly from the participant or by other means. Note that reporting procedures vary dependent on the nature of the incident (i.e. "serious" events are to be reported to LCTC in an expedited manner). Any questions concerning adverse event reporting should be directed to the LCTC in the first instance. A flowchart is given below to aid in determining reporting procedures for different types of adverse events.

Flowchart for Site Reporting Requirements of Adverse Events

Reporting Safety Events to the LCTC

All safety events (whether or not assessed as serious / related / expected) should be recorded on an Adverse Event Form; multiple events can be recorded on one form.

Safety events which are assessed as "serious" must **also** be recorded in more detail on Serious Adverse Event Forms; a single form is used for each individual event (i.e. a single diagnosis), though multiple symptoms can be recorded. Each SAE should have a corresponding record on the participant's AE form. Where additional information is received by site after initial submission to LCTC, this should be provided on a follow-up form within 5 days. Serious Adverse Event Forms collect data regarding the nature of event, date of onset, severity, corrective therapies given, outcome and causality; all serious events reported to LCTC will be reviewed by the Chief Investigator or Medical Reviewer/Clinical Coordinator, and assessed for causality and expectedness.

Follow-up after Adverse Events

All reportable adverse events should be followed until satisfactory resolution or until the investigator responsible for the care of the participant deems the event to be chronic or the participant to be stable.

When reporting “serious” safety events the investigator responsible for the care of the participant should apply the following criteria to provide information relating to event outcomes:

- resolved
- resolved with sequelae (specifying with additional narrative)
- not resolved/ongoing
- ongoing at final follow-up
- fatal or unknown.

11.2 Investigator Reporting Responsibilities

The PI is responsible for ensuring that all safety events requiring recording on this study which the local research team becomes aware of are reported to LCTC. It is the responsibility of the PI/Co-PI as recorded on the Delegation Log (medically qualified person) to assess the seriousness and causality of events.

All safety events must be recorded on an AE form and transferred to LCTC **within seven days of the site team becoming aware of the event.**

Safety events which meet the definition of “serious” must be reported in more detail to the LCTC on an SAE form and reported **immediately and in no circumstances later than 24 hours from becoming aware** unless the SAE is specified in the protocol as not requiring immediate reporting where they will be appropriately processed.

The SAE form should be completed by an appropriately delegated member of the research team; the assessments of seriousness and causality must be performed by an appropriately medically qualified person. Minimum reporting information must be provided in initial reports for all studies.

Minimum information required for reporting:

• Study identifier• Study centre• Patient number• A description of the event• Date of onset• Current status	
• Whether study treatment was discontinued• The reason why the event is classified as serious• Investigator assessment of the association between the event and study treatment
--	---

N.B. In the absence of a delegated medically qualified person the form should be completed and signed by an alternative member of the research site study team and submitted to the LCTC. As soon as possible thereafter the responsible investigator should check the SAE form, make amendments as appropriate, sign and re-send to the LCTC. The initial report shall be followed by detailed follow-up reports as appropriate.

Safety events should be reported to the site R&D team in accordance with local policy.

11.2.1 Reporting an Initial or Follow-up SAE

The investigator should ensure the actions below are completed for all reportable SAEs:

- 1) Research sites should telephone the appropriate study co-ordinator / data manager on [contact]** to advise that an SAE report has been submitted as soon as possible.

- 2) The SAE form should be transferred securely to [contact] (within 24 hours) to the CTU
- 3) The responsible investigator must notify their R&D department of the event (as per standard local governance procedures).
- 4) The participant must be identified by study number, age or month and year of birth and initials **only**. The participant's name **should not** be used on any correspondence.
- 5) SAEs must be subsequently followed up in line with the processes below:
 - Follow up must continue until clinical recovery is complete and laboratory results have returned to normal, or until the event has stabilised (see Section 11.7.4). N.B. Follow-up may continue after completion of protocol treatment if necessary.
 - Follow-up information is noted on a new SAE form to be transferred securely to the CTU as soon as more information becomes available
 - Tick the appropriate box on the new SAE form to identify the type of report; this is dependent on resolution status of the SAE e.g. follow-up / final.
- 6) Extra, annotated information and/or copies of anonymised test results may be provided separately.

Participant safety incidents that take place in the course of research should be reported to the National Reporting and Learning System (NRLS) by each participating NHS Trust in accordance with local reporting procedures. This also includes reporting any NIMPs.

11.3 LCTC Responsibilities

The study Sponsor, University of Liverpool, have delegated to LCTC the duty of onward reporting of safety events to REC, regulatory authorities. SOPs will be followed to ensure appropriate reporting as detailed below.

All “serious” safety events will be forwarded to the Chief Investigator or Medical Reviewer/Clinical Coordinator by LCTC within 24 hours of receiving the minimum information from site. The CI or Medical Reviewer/Clinical Coordinator will review information provided by site and for all events assessed as “related” will provide an assessment of “expectedness”.

Safety events which are assessed as “serious”, “related” and “unexpected” (i.e. RUSAEs) will be onward reported by LCTC to the ethics committee **within 15 days** of the LCTC first becoming aware of the event.

Additionally, RUSAEs will be reported to the study Sponsor(s) and Principal Investigators of participating sites.

A list of all safety events recorded for the study will also be reported annually by LCTC to the ethics committee and Independent Data Safety & Monitoring Committee.

Any concerns raised by the TSC/IDSMC or inconsistencies regarding safety reporting noted at a given site may prompt additional training at sites, with the potential for the LCTC to carry out site visits if there is suspicion of unreported AEs and SAEs in participant case notes. Additional training will also be provided if there are unacceptable delays in safety reporting timelines.

Safety Reports

Safety reports will be generated during the course of the study which allows for monitoring of safety event including reporting rates and safety events by participant group. The LCTC will send Annual Progress Reports (APRs) containing a list of all SAEs to the IDSMC, regulatory authorities and main REC. If any safety reports identify issues that have implications for the safety of study participants, the PIs at all institutions participating in the study will be notified.

Urgent Safety Measures (USMs)

An urgent safety measure (USM) is a procedure to protect clinical study participants from any immediate hazard to their health and safety but has not previously been defined by the protocol. It can be put in place prior to authorisation by the REC.

The LCTC will notify the REC immediately and, in any event, within 3 days that such a measure has been taken and the reasons why it has been taken. The initial notification to the REC will be by telephone (ideally within 24 hours) and a notice in writing will be sent within 3 days, setting out the reasons for the USM and the plan for further action. After discussion with the REC, further action will be agreed, which may include submission of a substantial amendment, a temporary halt, or permanent termination of the study.

Following notification, if a substantial amendment is required this must be submitted as soon as possible to the REC. If the study is temporarily halted it may not recommence until authorised to do so by the REC. If the study is permanently terminated before the date specified for its conclusion (in the original applications to REC), the Sponsor should notify the REC within 15 days of the date of termination by submitting the formal End of Study Notification.

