7.7 Concomitant Medications/Treatments and Specific Restrictions

This study is being conducted in healthy volunteers where the need for other medication is anticipated to be low. If an incidental diagnosis is made during the study (e.g. depression, hypertension) requiring drug treatment the CI/PI will review the individual situation and take a decision as to whether the participant should continue in a study. If the new medication required is not immunomodulatory, the presumption will be to continue in the study. Additional flavivirus vaccines should not be given during the study, but can be given once 8 weeks from the final dose of study vaccine has elapsed.

Medications Permitted

Permitted 'rescue' therapy (paracetamol, NSAIDs and anti-emetics) may be taken for either study related AEs or for any other reason, without the need to inform the investigators. All use of concomitant medication will be recorded throughout the study duration. The local PI and CI will need to be informed of any other medication needed during the study. The potential effects of concomitant medication will be reviewed by the investigators who will decide, along with the CI, whether the participant should remain in the study on a case by case basis.

Medications Not Permitted/ Precautions Required

Certain classes of medications, which would be expected to impair or alter immune responses, are not allowed to be taken during the study. These are:

- Corticosteroids, including inhaled steroids
- Colchicine
- Azathioprine, other cell cycle inhibitors, or chemotherapy agents

- Methotrexate or other anti-metabolites
- Any biologic immunosuppressive or immunomodulatory drug
- Insulin/OHGD
- Any vaccine other than those being given as part of the study

In the case of a participant needing such medication, the local PI and CI will review the case and decide whether to replace the participant or not. For example, if a participant has provided samples early in the study, replacement may not be necessary.

Data on Concomitant Medication

Data on Concomitant Medication

Participants will be asked to keep a diary of any other medicine use while they are taking part in the study. This will be reviewed by a member of the core clinical research team at each of the study visits.

Specific Requirements/Restrictions

Participants will be asked to follow some restrictions:

	Further details	Why

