9.5 Schedule for Assessments and Follow-up

Participants recruited into **Group 1** will remain on the study for 28 days post vaccination. Participants recruited into **Group 2** and **Group 3** will remain on the study for 8 weeks post vaccination. Once consented to take part in the main study, participants will receive the first dose of the vaccine at baseline following the completion of final eligibility checks and the collection of a baseline blood sample. Following this, participants will be asked to attend further clinic visits at the CRU on days 5 through 9 after vaccination for group 1, and at weeks 1, 2, 4 and 8 for groups 2 and 3, so that blood samples can be taken (55 – 75ml per visit) and any AEs can be assessed and recorded. T cell IFN γ -ELISpot intracellular cytokine staining (ICS) and flow cytometry assays will be performed at baseline and at weeks 1, 2, 4 and 8 after the vaccine in **Groups 2 and 3** participants, and at baseline and one week after the vaccine in **group 1**. Cells will be stained for plasmablast sorting for B cell ELISpot and single cell sequencing for assessment of the adaptive immune response at every timepoint for group 1, and at one week post vaccine for groups 2 and 3. Where possible, and where responses are identified, these will be mapped down to the peptide and later minimal epitope level and further characterised. Although the most crucial data regarding cross-reactivity are derived from the time point when responses are maximal (usually 1-2 weeks), the timing of responses can vary and these experiments have not been done in this population before, leading to uncertainty about when the maximal response is. For this reason, the assays will continue until week 8 post vaccine.

Details of the blood samples and volumes to be taken are shown in the Schedule of Assessments tables below. A slightly larger sample will be taken at week 1 post vaccine, to allow for single cell sorting of plasmablasts necessary to clone antibodies which will be performed at this time point. This time point can be revised based on the findings of group 1.

Schedule of Assessments:

Group 1

	Screening	Baseline*/ SV1	SV2	SV3	SV4	SV5	SV6
Timepoint			day 5	day 6	day 7	day 8	day 9
Procedures							
Signed Consent	X						
Assessment of Eligibility	X	X					
Review of Medical History	X	X					
Travel History	X	X	X				
Review of Concomitant Medications	X	X	X	X	X	X	X
Physical Exam	Complete	X					
	Symptom Directed		X			X	
	Vital Signs	X					

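### No adverse event assessment is scheduled between vaccination and day 5 (Group 1) or day 7 ±1 (Groups 2 and 3), and visit frequency then differs between Group 1 and the other groups

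*Protocol*

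**What the plan says.** Protocol section 9.5 schedules clinic visits "on days 5 through 9 after vaccination for group 1, and at weeks 1, 2, 4 and 8 for groups 2 and 3". Blood is drawn at these visits, and "any AEs can be assessed and recorded". The schedule table gives the week 1 visit in Groups 2 and 3 a window of day 7 ±1, and the text adds: "This time point can be revised based on the findings of group 1". A footnote to the table puts all baseline procedures before the vaccine is given.

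Section 9.5 also requires the onset, duration and severity of each event to be documented. It encourages participants to report events unprompted between visits and gives them a card with a 24-hour number. Section 10.6 sets the monitoring period at 28 days and asks Group 1, whose last visit is day 9, to telephone with later events.

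The only diary is described in section 7.7: "Participants will be asked to keep a diary of any other medicine use while they are taking part in the study". It is reviewed at each visit. The same section says that permitted rescue drugs "may be taken for either study related AEs or for any other reason, without the need to inform the investigators", and then that all concomitant medication use is recorded throughout the study.

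Under Safety Reports, section 11.3 provides for "monitoring of safety event including reporting rates and safety events by participant group". Section 4.4 says safety will be monitored to the standard of a late-phase trial.

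**The concern.** Table 2 in section 4.3.1 lists tiredness, feeling unwell, injection site pain, headache and muscle pain as very common after this vaccine. Where such reactions begin in the first days, no scheduled contact asks about them at the time. Healthy volunteers may not telephone a 24-hour emergency number about a sore arm. Whatever is not volunteered must be recalled days later, although the protocol wants onset and duration recorded.

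In addition, Group 1 is asked about events daily on days 5–9, while Groups 2 and 3 are asked once in that period. A report by participant group then sets side by side counts collected with different intensity. What is at stake is the completeness of early safety data and the reading of Group 1 against the other two groups. No efficacy or immunology conclusion depends on it.

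**Working it through.** **Inputs.** Visit days from section 9.5: Group 1 on days 5, 6, 7, 8 and 9; Groups 2 and 3 on days 7, 14, 28 and 56 (nominal). Blood volumes come from the schedule tables and section 9.6, group sizes from section 12.2.

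**Check of the visit counts against the stated blood volumes.** A standard draw is 3.7 + 2.5 + 8.5 + 40 = 54.7 ml; the week 1 draw in Groups 2 and 3 is 3.7 + 2.5 + 8.5 + 60 = 74.7 ml.
- Group 1, six draws including baseline: 6 × 54.7 = 328.2 ml (stated: 330 ml).
- Groups 2 and 3, five draws including baseline: 4 × 54.7 + 74.7 = 293.5 ml (stated: about 300 ml).

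The stated volumes agree with five post-vaccination visits in Group 1 and four in Groups 2 and 3.

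**Scheduled AE assessments after vaccination, per participant.**

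| Days | Group 1 | Groups 2 and 3 |
|---|---|---|
| 1–4 | 0 | 0 |
| 1–9 | 5 | 1 |
| 10–28 | 0 | 2 |
| 1–28 | 5 | 3 |
| 1–56 | 5 | 4 |

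The ±1 day window on week 1 does not change the count through day 9. The week 4 visit has a ±3 day window; if it falls on days 29–31, the entries for days 10–28 and 1–28 become 0 v 1 and 5 v 2. Baseline adds nothing, because its procedures precede the vaccine.

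**Interval from an event to the first scheduled question.**
- Event on day 0: 5 days in Group 1; 6–8 days in Groups 2 and 3.
- Event on day 1: 4 days; 5–7 days.
- Event on day 4: 1 day; 2–4 days.

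**Illustration of the effect on capture.** Assume each visit independently elicits a mild early event with probability p, and ignore spontaneous reports. Capture after n visits is 1 − (1 − p)^n.
- p = 0.5: by day 9, 1 − 0.5^5 = 97% in Group 1 v 50% in Groups 2 and 3; by day 28, 1 − 0.5^3 = 88% in Groups 2 and 3.
- p = 0.9: by day 9, above 99.9% v 90%; by day 28, 99.9% in Groups 2 and 3.
- p = 1: no difference.

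The protocol gives no value of p, so this shows a range and estimates nothing.

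**Weight of one event.** One additional participant with an event moves a group proportion by 1/4 to 1/3 (25 to 33 percentage points) in Group 1, 1/10 to 1/6 (10 to 17) in Group 2, and 1/12 to 1/8 (8 to 12.5) in Group 3.

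**The case against.** The strongest reply is that the protocol does provide routes for early events: spontaneous reporting at any time, a 24-hour number, and a medicine diary reviewed at each visit that could prompt a question about why a drug was taken. No primary or secondary endpoint exists, comparisons are post hoc and exploratory (section 5), and the text in section 11.3 describes ongoing monitoring. In that text, the words about participant group may attach to safety events and not to reporting rates. All of this stands, and it confines the point to missing structured solicitation and limited comparability.

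A reader might infer more in five ways that the documents do not support:

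- **That unequal questioning could pass for an effect of previous flavivirus exposure.** Group 1 takes any exposure status, so its contrast with the others is not an exposure contrast. Naïve v experienced is Group 2 v Group 3, which follow an identical schedule.
- **That Group 1 rates must come out higher.** Only the opportunity to report differs by design. A worsening event updates its existing record (section 10.6), so repeated visits need not mean repeated counts. The balance of visits also reverses after day 9.
- **That the gap matters because it spans most of the viraemic period.** The statement "This lasts up to 6 days after vaccination" is made about pregnancy risk, and nothing ties it to the timing of reactions.
- **That the stopping scenarios in section 9.8 are compromised.** The one needing two or more participants concerns clinically relevant or intolerable events that the chief investigator thinks warrant stopping. Forgotten mild reactions would hardly meet it.
- **That rescue drugs go unrecorded.** The wording may mean only that no prior notice is needed, since the next sentence has all use recorded. The two statements still read against each other.

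**Conclusion.** The point holds in a limited form. No AE assessment is scheduled from vaccination until day 5 in Group 1 or day 7 ±1 in Groups 2 and 3, and no symptom diary is described, so capture on days 0–4 depends on spontaneous reports or later recall. Scheduled opportunities to report, Group 1 v Groups 2 and 3, are 5 v 1 through day 9, 0 v 2 on days 10–28 and 5 v 3 over 28 days. Visit-elicited rates in Group 1 are therefore not comparable with those in the other groups. The size and direction of any resulting difference cannot be derived from the protocol, and the contrast between Groups 2 and 3 is untouched.

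This rests on nominal visit days, on the week 1 visit staying near day 7 (section 9.5 allows it to be revised), and on there being no solicitation procedure outside the text at hand. It is an inexpensive improvement to safety capture and does not threaten the study's scientific aims.

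**What to change.** 1. **Sections 7.7 and 9.5:** add a daily symptom section (onset, duration, severity) to the existing diary, from day 0 to at least day 9, in all three groups, reviewed at the next visit.
2. **Section 11.3:** in reports by group, show diary-solicited events over that common window separately from visit-elicited and spontaneous events, and state that visit-elicited rates in Group 1 are not comparable with those in Groups 2 and 3.
3. **Section 7.7:** reconcile the statement that rescue drugs need not be notified to the investigators with the statement that all concomitant medication is recorded.

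No extra visits or blood are needed. The cost is one section in a diary participants already keep, slightly more data entry, and a higher recorded count of mild events, which the reports should explain.
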